The primary outcome of the trial will be the pathologic changes that result from bronchoscopic laser ablation of peripheral lung tumors, and will be categorized into three groups: 1. Complete Ablation: absence of staining (MAB 1273 or NADH, or both) of tumor cells. 2. Quasi-Complete Ablation: positive staining of $\leq 10\%$ of tumor cells. 3. Incomplete ablation: positive staining in $> 10\%$ of tumor cells. The secondary outcomes include the safety of this ablative procedure which will be measured by serious adverse effects (SAE), defined as pneumothorax requiring chest tube, bleeding requiring balloon tamponade or leading to respiratory failure, and hypoxemia ($\text{SpaO}_2 < 90\%$ for > 1 min) during bronchoscopy, post-bronchoscopy pneumonitis with need of supplemental oxygen., as well as pathologic changes observed in the lung tissue surrounding the treated lung tumor, and radiographic changes observed by cone-beam CT immediately after the application of bronchoscopic laser ablation.

Only patients who undergo bronchoscopic tumor ablation will be included in the analysis.

We will conduct extensive descriptive analyses of the data collected. We will calculate the appropriate summary statistics and 90% confidence intervals (CIs) for the measures of interest described in primary and secondary objectives. For example, we will obtain frequencies and proportions of the three tumor ablation outcome categories (complete, quasi-complete, and incomplete) for the primary objective, and record the number of each type of SAE at each level of laser power. Our goal is to simply assess the magnitude and obtain preliminary estimates of this technique to proceed to our next project which is the development of a large multicenter randomized trial comparing the effectiveness of this new bronchoscopic laser ablative technique vs. the standard of care for these patients, SBRT, in patients with medically inoperable early lung cancer.

[figure not shown]

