Sample Size Justification. This is a pilot trial to assess whether a new technique can be delivered safely to humans and provide complete ablation of lung tumors, and is not powered for significance in statistical comparison as there is insufficient existing evidence to predict the likely outcomes. A total of 15 patients will be recruited from UT MD Anderson Cancer Center. With this sample size, the 90% confidence interval for an expected 70% of complete ablation rate can be estimated with a maximum width of 0.195. This power was based on nQuery Advisor.

Toxicity Monitoring

[figure not shown]
We will monitor patients for unacceptable toxicity in cohorts of size 5 [11]. An unacceptable toxicity in this study is defined as pneumothorax requiring chest tube, bleeding requiring balloon tamponade or leading to respiratory failure, and hypoxemia ($\text{SpaO}_2 < 90\%$ for > 1 min) during bronchoscopy, post-bronchoscopy pneumonitis with need of supplemental oxygen.

If we find $\text{Pr}[\pi_T > 0.3 | \text{data}] > 0.85$, where π_T is the true proportion of patients who experience unacceptable toxicities and follows a $\text{beta}(0.6, 1.4)$ distribution, we will stop the trial for toxicity.

The stopping boundaries for toxicity are found in Table 1. Table 2 shows the operating characteristics for this design. The stopping boundaries and operating characteristics were created based upon 1,000 simulations using Multc Lean Desktop V2.1.

Other Considerations

REFERENCES

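### The toxicity stopping rule counts only four listed events, so a procedure-related death or life-threatening event outside the list is scored as no toxicity and moves the rule away from stopping

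*Combined protocol and SAP*

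**What the plan says.** The Sample Size Justification describes a pilot whose purpose is "to assess whether a new technique can be delivered safely to humans" and to achieve complete ablation. It plans 15 patients.

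Under Toxicity Monitoring, "We will monitor patients for unacceptable toxicity in cohorts of size 5". The definition reads "An unacceptable toxicity in this study is defined as pneumothorax requiring chest tube, bleeding requiring balloon tamponade or leading to respiratory failure". It then adds oxygen saturation below 90% for more than one minute, and ends "during bronchoscopy, post-bronchoscopy pneumonitis with need of supplemental oxygen". The list stops there. It has no catch-all, and neither death nor life-threatening events are mentioned.

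The trial stops for toxicity if the posterior probability that the rate exceeds 0.3 is above 0.85, starting from a beta(0.6, 1.4) prior. The monitored rate "is the true proportion of patients who experience unacceptable toxicities".

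The Statistical Considerations text uses the same list for its safety outcome, "measured by serious adverse effects (SAE), defined as pneumothorax requiring chest tube, bleeding requiring balloon tamponade or leading to respiratory failure", followed by the same hypoxemia and pneumonitis items. Secondary objective 2a is worded more openly, giving bleeding, pneumothorax, fever and pneumonitis as examples, but it only describes complications and does not feed the rule.

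**The concern.** The rule has two bins, toxicity and no toxicity, and the definition decides which bin each treated patient enters. Respiratory failure counts only if bleeding led to it. Hypoxemia counts only during the bronchoscopy. After the procedure, the only item explicitly placed there is pneumonitis needing oxygen. A patient who dies of, or is put at risk of death by, a procedure-related event with none of the listed features goes into the no-toxicity bin. That is not neutral: the patient adds to the denominator, so the posterior moves towards safety.

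The Sample Size Justification itself says there is too little evidence to predict the likely outcomes. A closed list presumes that the serious harms are already known. A report that the boundary was not crossed would be silent about serious harms outside the list, although the results are meant to support a large randomized trial.

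**Working it through.** **Inputs** (all from Toxicity Monitoring and Sample Size Justification): prior beta(0.6, 1.4); limit 0.30; cut-off 0.85; cohorts of 5; maximum 15 patients, hence looks at 5, 10 and 15. The four items are read as any one of them, the only workable reading. Tables 1 and 2 are cited, but their figures are not in the available text, so there is no stated boundary to reproduce. The boundaries below are derived.

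**Posterior.** With x toxicities in n patients the posterior is beta(0.6 + x, 1.4 + n − x), and the monitored quantity is its probability above 0.30.

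| n | Largest x that continues | Smallest x that stops |
|---|---|---|
| 5 | 2 (0.626) | 3 (0.875) |
| 10 | 4 (0.711) | 5 (0.880) |
| 15 | 6 (0.766) | 7 (0.893) |

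**Effect of one unlisted event scored as written.**
- Before any data the probability is 0.417. One patient scored as a non-event takes it to 0.258.
- 2/4 gives 0.734. A fifth patient with only an unlisted event makes it 2/5 = 0.626, continue. Counted, it is 3/5 = 0.875, stop.
- 4/9 gives 0.782. A tenth such patient makes it 4/10 = 0.711, continue. Counted, it is 5/10 = 0.880, stop.

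The values at 4 and 9 patients are not looks. They only show the direction of movement. If no listed event occurs at all, x stays at 0 and the rule cannot stop, whatever else happens.

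**Chance of stopping by patient 10.** The look at 15 comes after full accrual, so the first two looks are the ones that can spare patients. For a per-patient event rate p:

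P(stop) = P(X ≥ 3) + Σ over x = 0, 1, 2 of P(X = x) × P(Y ≥ 5 − x), with X and Y independent binomial(5, p).

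At p = 0.20 the first term is 0.0579. The second is 0.3277 × 0.0003 + 0.4096 × 0.0067 + 0.2048 × 0.0579 = 0.0147. The total is 0.0726, or 7.3%.

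The documents give no event rates, so the next step rests on assumptions: listed events at 20%, unlisted fatal or life-threatening events at rate u, independent of each other. If both are counted, p = 1 − 0.80 × (1 − u).

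| u (assumed) | p if all counted | Stop by 10, as written | Stop by 10, all counted |
|---|---|---|---|
| 1% | 0.208 | 7.3% | 8.1% |
| 2% | 0.216 | 7.3% | 9.1% |
| 5% | 0.240 | 7.3% | 12.2% |
| 15% | 0.320 | 7.3% | 26.6% |
| 30% | 0.440 | 7.3% | 54.8% |

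The last two rows show how the gap grows. Nothing in the documents suggests rates that high.

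**What counting would not do.** With the same boundaries, one event in five gives 0.284 and two give 0.626. Both continue.

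**The case against.** The strongest reply is that the available text has visibly lost content. The heading Other Considerations stands empty directly after Toxicity Monitoring, the part between the exclusion criteria and the statistics is replaced by an unrelated table, and Tables 1 and 2 are absent. Adverse-event reporting, oversight or a separate rule for deaths may sit there. This stands. A reader might infer that the trial has no safeguard against an unlisted death, and the documents do not support that. Other oversight would not, however, change the definition that feeds this rule.

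Second, many catastrophes already count. Any event that takes saturation below 90% for over a minute during bronchoscopy qualifies, as does bleeding that leads to respiratory failure. This also stands and narrows the gap to events without those features, mainly after the procedure.

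Third, a 0.30 limit on a composite is a weak tool for fatal events, as the 0.284 and 0.626 above show. That is correct. The point is that such an event should not count as evidence of safety, not that adding it would make the rule sensitive to single deaths.

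Fourth, naming expected procedure-specific toxicities is a legitimate design choice that no other section contradicts. That is fair as to the list, but it does not justify the direction in which an unlisted death moves the posterior.

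A reader might also infer that the trial could run to the end with a harm rate above its own limit because of the list. The 0.30 limit was set for the listed events, not for all harm. Even with everything counted at a 32% total rate, the rule fails to stop by patient 10 in 100 − 26.6 = 73.4% of trials, which reflects mainly the small sample.

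**Conclusion.** The concern holds in a limited form. Followed exactly, the rule scores a patient whose sole event is an unlisted procedure-related death or life-threatening event as no toxicity, and the posterior falls. That follows from the stated definition and prior and needs no assumed rate. When two listed events have already occurred in the first cohort, the scoring of one such patient decides between continuing (0.626) and stopping (0.875).

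The average effect is modest at low unlisted rates: 7.3% against 8.1% to 12.2% for stopping by patient 10, with unlisted rates of 1% to 5%. These figures rest on an assumed 20% listed rate, independence and boundaries derived without Table 1. Larger gaps need unlisted rates that the documents do not support. The change is worth making because it is cheap and corrects the direction of the rule.

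**What to change.** In Toxicity Monitoring, amend the definition of unacceptable toxicity so that a death or life-threatening event judged at least possibly related to the study procedure is not scored as a non-event. The exact event wording is for the sponsor and investigator to settle. Align the identical SAE list in the Statistical Considerations text with it, so that what is reported and what is monitored agree.

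Keep the prior, the 0.30 limit, the 0.85 cut-off and the boundaries, none of which depends on which events are listed. State openly that this composite rule would still not stop on one or two such events in five patients (0.284 and 0.626), and refer to any separate handling of deaths if it exists elsewhere in the protocol.

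The cost is a sentence or two of text, with no extra patients, visits or procedures. Relatedness must be judged for events outside the present list, and stopping becomes slightly more likely.
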